#### 1. Introduction

This study is a multisite, randomized, double-blind, placebo-controlled trial comparing efficacy and safety of prazosin versus placebo in AD patients with disruptive agitation either in long-term care or home-dwelling with a caregiver.

#### 1.1 Randomization / Study Design

In this randomized, double-blind study design, eligible participants per site will be randomized using a 2:1 schedule to either the prazosin or placebo groups, and stratified by gender.

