#### 4. Efficacy Analysis

#### 4.1 Analysis of the Primary Outcome

Hypothesis 1a: Participants randomized to prazosin will manifest greater benefit on the primary outcome measure – the ADCS-Clinical Global Impression of Change in Agitation (ADCS-CGIC-A) anchored to disruptive agitation. The ADCS-CGIC-A is a 7-point scale that is structured as the clinician's assessment of change from baseline compared to the ADCS-CGIC-A Baseline Worksheet. A score of 1-2 indicates clinically meaningful improvement; a score of 3-5 indicates no clinically meaningful change; a score of 6-7 indicates clinically meaningful worsening.

The mITT data set will be used for primary analysis in this study. To address the aims for the primary efficacy analysis (Hypothesis 1a), longitudinal ADCS-CGIC-A scores from first post-baseline visit through 12 weeks will be analyzed using a mixed effects model for repeated measures (MMRM) to assess differences in ADCS-CGIC-A. The MMRM will include terms for time, intervention, intervention-by-time interaction plus covariates gender and severity of agitation at baseline defined as CMAI score. Time will be treated as categorical.

Differences in the primary outcome, ADCS-CGIC-A, between intervention groups will be tested at the two-sided 5% significance level. No adjustment to the type 1 error level will be made for secondary analyses.

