#### 4.2 Analysis of Secondary Outcomes

Hypothesis 1b: Participants randomized to prazosin will manifest greater benefit on the key secondary outcome measure – the Neuropsychiatric Inventory (NPI)/Neuropsychiatry Inventory-Nursing Home version (NPI-NH). Similar analyses to that described for the primary analysis will be performed on the total scores of the NPI/NPI-NH. An MMRM analysis as described above for the primary outcome measure will compare prazosin vs placebo at 12 weeks.

Hypothesis 1c: Participants randomized to prazosin will receive a lower cumulative total dose of lorazepam "rescue medication" administered during the trial. Similar analyses to that described for the primary analysis will be performed on the total dose of rescue lorazepam. Multiple linear regression

analysis will compare prazosin vs placebo through at 12 weeks. Gender and severity of agitation at baseline as measured by the CMAI will be included as covariates.

Hypothesis 1d: Study discontinuation ("dropout") due to persistent or worsening intolerable disruptive agitation will occur sooner in the placebo group than in the prazosin group. A Cox proportional hazards model will be used to compare the median time to dropout between groups adjusting for covariates (i.e., gender and baseline CMAI score). Those individuals who dropout for drug intolerance will be censored within this analysis according to their time from randomization to their last observation on protocol.

Hypothesis 1e: There will be larger proportion of responders to prazosin (defined as moderate or marked improvement) vs non-responders (defined as minimal improvement; no change; or minimal, moderate, or marked worsening) on the ADCS-CGIC-A. A logistic regression model including covariates of gender and baseline severity on CMAI will be used to compare percent of responders (ADCS-CGIC-A scores of 1 and 2) vs minimal or no change (ADCS-CGIC-A scores of 3, 4, and 5) vs worsening (ADCS-CGIC-A scores of 6 and 7).

Hypothesis 2: Participants randomized to prazosin will manifest greater benefit on the modified ADCS-Activities of Daily Living-Severe Dementia version (ADCS-ADL-Severe). Similar analyses to that described for the primary analysis will be performed on the ADCS-ADL-Severe. An MMRM analysis using the model specified for the primary outcome measure above will compare prazosin vs placebo at 12 weeks.

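### Participants are randomized within site and by gender, but only gender of these two factors enters the models; a random site intercept would recover a little power cheaply if sites differ in their ratings

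*SAP*

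**What the plan says.** - **Design.** SAP section 1 opens with "This study is a multisite, randomized, double-blind, placebo-controlled trial". Section 1.1 adds that "eligible participants per site will be randomized using a 2:1 schedule to either the prazosin or placebo groups, and stratified by gender". The number of sites is not given.
- **Primary model, section 4.1.** "The MMRM will include terms for time, intervention, intervention-by-time interaction plus covariates gender and severity of agitation at baseline defined as CMAI score". There is no site term, fixed or random, and no degrees-of-freedom method is named.
- **Secondary models, section 4.2.** For the rescue lorazepam regression: "Gender and severity of agitation at baseline as measured by the CMAI will be included as covariates". The Cox model is described as "adjusting for covariates (i.e., gender and baseline CMAI score"). The responder analysis is "A logistic regression model including covariates of gender and baseline severity on CMAI". The MMRMs for the NPI/NPI-NH total, ADCS-ADL-Severe and caregiver distress scores refer back to the primary model.
- **Exploratory models, section 4.3.** The five-domain NPI analysis uses the primary model. The CMAI analysis names gender as its only covariate.

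No reason for leaving site out is given. Section 2 reduces the trial to a pilot of 25 to 80 participants and expects the longitudinal analysis to be more powerful than the t-tests used for sizing.

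**The concern.** When allocation is balanced within groups, the treatment contrast varies only through the differences inside those groups. A model that ignores the groups still counts the differences between them as noise, so its standard error is too large. The SAP follows this logic for gender but not for site.

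Site is a plausible source of variance here because the primary outcome is a clinician's global rating of change, and ratings made at one site may share a rater's habits. At stake is precision, in a trial that has already given up its larger target and looks to the final model for extra power.

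**Working it through.** **1. The plan's own figure.** For an effect of 0.71 SD and 2:1 allocation, section 2 gives 80 participants (53 + 27). I carry over alpha 5% two-sided, power 80% and dropout 10% from the initial sizing in the same section. The control group needs (1 + 1/2) × (1.960 + 0.842)² / 0.71² = 1.5 × 7.85 / 0.504 = 23.4, so 24. The total is 3 × 24 = 72, and 72 / 0.9 = 80, which reproduces. The same route gives 80, 64, 50, 40 and 30 against the stated 80, 65, 50, 40 and 30. None of this sizing has a site component.

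**2. What omitting site does, in closed form.** Let the total variance be 1 and the between-site share be ICC = ρ (assumed). With exact balance within sites, the true variance of the treatment difference is (1 − ρ)(1/n1 + 1/n2), while a model without site reports about (1/n1 + 1/n2).

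- After 10% dropout, n1 = 47.7 and n2 = 24.3. The noncentrality is 0.71 × √(47.7 × 24.3 / 72) = 2.849, and the critical value on 70 df is 1.994.
- Power without site is about Φ[(2.849 − 1.994) / √(1 − ρ)].
- With site variance removed at no cost in degrees of freedom, the effect becomes 0.71 / √(1 − ρ), and noncentral-t power is used.
- Type I error without site is about 2Φ[−1.96 / √(1 − ρ)].

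| ICC | Power, no site | Power, site removed | Gain (points) | Type I error, no site |
|---|---|---|---|---|
| 0 | 0.80 | 0.80 | 0 | 5.0% |
| 0.05 | 0.81 | 0.82 | 1 | 4.4% |
| 0.10 | 0.82 | 0.84 | 3 | 3.9% |
| 0.20 | 0.83 | 0.88 | 5 | 2.8% |

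**3. Simulation at pilot sizes.** Settings: 2,000 trials per cell, 2:1 permuted blocks within site by gender, unequal site sizes, one continuous outcome. ICC and number of sites are assumed, and the ICC is treated as known in the random-intercept model. Cells show power (%) without site → with a random site intercept.

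| N analysed, effect | Sites | ICC 0 | ICC 0.05 | ICC 0.10 | ICC 0.20 |
|---|---|---|---|---|---|
| 72, 0.71 | 5 | 81.2 → 81.2 | 80.6 → 81.8 | 80.6 → 82.8 | 83.4 → 87.4 |
| 72, 0.71 | 15 | 81.8 → 81.8 | 81.0 → 82.0 | 81.2 → 83.4 | 81.4 → 86.0 |
| 36, 1.0 | 5 | 78.6 → 78.6 | 80.2 → 81.5 | 79.8 → 82.0 | 80.2 → 84.8 |
| 36, 1.0 | 15 | 78.0 → 78.0 | 77.8 → 78.5 | 78.1 → 80.0 | 77.7 → 82.6 |
| 27, 1.2 | 5 | 78.3 → 78.3 | 81.2 → 82.4 | 81.0 → 82.7 | 84.1 → 87.5 |
| 27, 1.2 | 15 | 77.4 → 77.4 | 78.6 → 79.4 | 78.2 → 79.6 | 81.4 → 84.6 |

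The gains are 0.7 to 1.3 points at ICC 0.05, 1.4 to 2.2 at 0.10, and 3.2 to 4.9 at 0.20. Type I error without site at ICC 0.20 is 2.8% to 4.4%.

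**4. With the site variance estimated by REML.** Enrolling 80 at 10 sites (effect 0.71), power without v with site is 79% v 80% at ICC 0, 80% v 83% at 0.10 and 81% v 86% at 0.20. Enrolling 40 at 8 sites (effect 1.0), it is 77% v 77%, 78% v 81% and 79% v 84%. A further run of 80 participants at 8 to 15 sites gave 81% v 86-87% at ICC 0.20, a gain of 5 to 6 points. Monte Carlo error is about 1 point per power figure, so 3 to 7 points at ICC 0.20 is the simulated range rounded outward.

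**5. Fixed site effects instead.** With 15 sites, power at N = 36 falls from 78% to 64% at ICC 0 and from 78% to 74% at ICC 0.20. At N = 27 it falls from 77% to 60% and from 81% to 71%.

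**The case against.** - **The current model is a legitimate choice.** It is pre-specified, unbiased and does not inflate false positives. This stands. A reader might infer that dropping a randomization factor invalidates the primary test or contradicts section 1.1. The document supports neither: the error is on the conservative side, and nothing in the SAP promises a site term.
- **Per site may only say where randomization happens.** The wording allows this. If allocation is not blocked within site, the test would sit nearer its nominal level, but site variance would still be in the residual and still cost power.
- **The loss is not established.** This also stands. It needs an ICC above zero, which the SAP does not give. The ADCS-CGIC-A is rated against each participant's own baseline worksheet, so a rater's constant severity may partly cancel. The SAP does not show one rater per site either.
- **The remedy is not free at the smallest sizes.** With the variance estimated and residual degrees of freedom, type I error at 12 sites and ICC 0 was 6.8% v 5.8% without site (N = 36) and 6.7% v 5.8% (N = 27), with Monte Carlo error about 0.5 points. Part of the small-sample gain may therefore be mild anti-conservatism. At N = 27 to 36 and ICC 0.05 to 0.10, the site variance was estimated at zero in about 33% to 52% of runs, so the new model often equals the present one.

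These points shrink the claim and shape the remedy. They do not remove the claim, since every set-up agrees in direction and rough size.

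**Conclusion.** The point holds as a cheap improvement. Site is used in the randomization and appears in no model. If sites differ in their ratings, the analysis is valid but conservative and loses some power: about 0 points at ICC 0, 1 to 3 at ICC 0.05 to 0.10, and 3 to 7 at ICC 0.20.

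These figures rest on an assumed ICC, an assumed number of sites (5 to 15) and a single time point rather than the full repeated-measures model, so they are indicative. A reader might also infer that the models adjust for gender only. That is true only of the two randomization factors, because the primary model and most others include baseline CMAI as well. Nor do the documents support saying that the standard error is too large as a matter of fact; it is so only if between-site variance exists.

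**What to change.** Add a random intercept for site to the primary MMRM in section 4.1 and to the secondary MMRMs that refer to it. Specify Kenward-Roger or a similar small-sample degrees-of-freedom method. State a numerical threshold and rule for pooling small sites, fixed before unblinding. If the site variance is estimated at zero, the model reduces to the current one. Do not use one fixed effect per site. If the team prefers to keep site out, one sentence giving the reason would do.

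The cost is one variance parameter, a pooling rule, and a check that the planned R code fits the site intercept alongside the within-participant covariance with the chosen degrees-of-freedom method. The remaining risk is slight anti-conservatism at about 25 to 40 participants if residual degrees of freedom are used. Pooling itself was not simulated.

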#### 2. Power and Sample Size Determination

Power calculations for PEACE-AD were based on two-sample t-tests. Sample sizes were initially estimated targeting a power=80%, assuming a 2-sided alpha=5%, a standardized effect size of .44 SDs, and a dropout rate of 10%. This is a reasonable estimate of attrition given the study population and the relatively short follow-up period. Based on these considerations, 186 total participants are required: 124 in the prazosin group, and 62 in the control group.

Following COVID-19 in March 2020, it became clear that it would not be possible to successfully recruit this sample size to this protocol. In turn, a decision was made to change the focus to being a pilot trial of between 25-80 participants, a target number that was considered feasible in the aftermath of the pandemic. The range of sample sizes were then considered as a function of the standardized effect size delta; for delta = .71 the required sample size is 80 (53 in the prazosin group, and 27 in the control group), for delta = .79 the required sample size is 65 (43 in the prazosin group, and 22 in the control group), for delta = .91 the required sample size is 50 (33 in the prazosin group, and 17 in the control group), for delta = 1.0 the required sample size is 40 (27 in the prazosin group, and 13 in the control group), for delta = 1.2 the required sample size is 30 (20 in the prazosin group, and 10 in the control group).

The statistical analyses at study conclusion will be based on longitudinal regression data analysis that is expected to increase statistical power over the initial estimates with two-sample t-tests.

#### 3. Selection of Participants to Be Used in Analysis

The intent-to-treat (ITT) data set will include all eligible individuals who are randomized. The modified ITT data set will include all eligible individuals who are randomized and reached the minimum allowed dose of 1mg BID). This definition has been adjusted from the protocol to allow the largest representation of treated participants who achieved a potentially therapeutic dose.

The per-protocol data set will include all eligible participants who: 1) complete the 12-week assessments for the primary analysis, and demonstrate 80% drug compliance as documented in medication administration records.

The modified ITT data set (mITT) will serve as the primary efficacy analysis. The ITT and per protocol analyses will also be performed as part of the secondary analytic plan.

#### 3.1 Safety Analysis Population

The safety analysis population is defined as those subjects that are randomized and took at least one dose of study drug. Categorical safety data will be analyzed, compared between treatment arms, using the exact contingency table method, Fisher's Exact Test.

#### 4. Efficacy Analysis

#### 4.1 Analysis of the Primary Outcome

Hypothesis 1a: Participants randomized to prazosin will manifest greater benefit on the primary outcome measure – the ADCS-Clinical Global Impression of Change in Agitation (ADCS-CGIC-A) anchored to disruptive agitation. The ADCS-CGIC-A is a 7-point scale that is structured as the clinician's assessment of change from baseline compared to the ADCS-CGIC-A Baseline Worksheet. A score of 1-2 indicates clinically meaningful improvement; a score of 3-5 indicates no clinically meaningful change; a score of 6-7 indicates clinically meaningful worsening.

The mITT data set will be used for primary analysis in this study. To address the aims for the primary efficacy analysis (Hypothesis 1a), longitudinal ADCS-CGIC-A scores from first post-baseline visit through 12 weeks will be analyzed using a mixed effects model for repeated measures (MMRM) to assess differences in ADCS-CGIC-A. The MMRM will include terms for time, intervention, intervention-by-time interaction plus covariates gender and severity of agitation at baseline defined as CMAI score. Time will be treated as categorical.

Differences in the primary outcome, ADCS-CGIC-A, between intervention groups will be tested at the two-sided 5% significance level. No adjustment to the type 1 error level will be made for secondary analyses.

#### 4.2 Analysis of Secondary Outcomes

Hypothesis 1b: Participants randomized to prazosin will manifest greater benefit on the key secondary outcome measure – the Neuropsychiatric Inventory (NPI)/Neuropsychiatry Inventory-Nursing Home version (NPI-NH). Similar analyses to that described for the primary analysis will be performed on the total scores of the NPI/NPI-NH. An MMRM analysis as described above for the primary outcome measure will compare prazosin vs placebo at 12 weeks.

Hypothesis 1c: Participants randomized to prazosin will receive a lower cumulative total dose of lorazepam "rescue medication" administered during the trial. Similar analyses to that described for the primary analysis will be performed on the total dose of rescue lorazepam. Multiple linear regression

analysis will compare prazosin vs placebo through at 12 weeks. Gender and severity of agitation at baseline as measured by the CMAI will be included as covariates.

Hypothesis 1d: Study discontinuation ("dropout") due to persistent or worsening intolerable disruptive agitation will occur sooner in the placebo group than in the prazosin group. A Cox proportional hazards model will be used to compare the median time to dropout between groups adjusting for covariates (i.e., gender and baseline CMAI score). Those individuals who dropout for drug intolerance will be censored within this analysis according to their time from randomization to their last observation on protocol.

Hypothesis 1e: There will be larger proportion of responders to prazosin (defined as moderate or marked improvement) vs non-responders (defined as minimal improvement; no change; or minimal, moderate, or marked worsening) on the ADCS-CGIC-A. A logistic regression model including covariates of gender and baseline severity on CMAI will be used to compare percent of responders (ADCS-CGIC-A scores of 1 and 2) vs minimal or no change (ADCS-CGIC-A scores of 3, 4, and 5) vs worsening (ADCS-CGIC-A scores of 6 and 7).

Hypothesis 2: Participants randomized to prazosin will manifest greater benefit on the modified ADCS-Activities of Daily Living-Severe Dementia version (ADCS-ADL-Severe). Similar analyses to that described for the primary analysis will be performed on the ADCS-ADL-Severe. An MMRM analysis using the model specified for the primary outcome measure above will compare prazosin vs placebo at 12 weeks.

Hypothesis 3: Participants randomized to prazosin will have a greater reduction in the NPI/NPI-NH "caregiver distress"/ "occupational disruptiveness" score. Similar analyses to that described for the primary analysis will be performed on the NPI/NPI-NH "caregiver distress"/ "occupational disruptiveness" score. An MMRM analysis using the model specified for the primary outcome measure above will compare prazosin vs placebo at 12 weeks.

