#### 4.3 Analysis of Exploratory Outcomes

Hypothesis 4: Participants randomized to prazosin will manifest greater benefit on the CMAI. Similar analyses to that described for the primary analysis will be performed on the CMAI. An MMRM analysis including gender as a covariate will compare prazosin vs placebo at 12 weeks.

Hypothesis 5: Improvement in the five domain NPI/NPI-NH subset score (Agitation/Aggression, Anxiety, Disinhibition, Irritability/Lability, and Aberrant Motor Behavior) will have a greater effect size in response to prazosin treatment than the 12-domain NPI/NPI-NH total score. An MMRM analysis using the model specified for the primary outcome measure above will compare prazosin vs placebo at 12 weeks.

Hypothesis 6: Participants randomized to prazosin will manifest greater improvement in sleep continuity during the 12-hour nighttime period and at each week during the 12-week study duration. Improvement in the primary actigraphy outcome measures will be defined as a decrease in locomotor

activity as assessed by total activity counts over the 24-hour period, specifically a decrease in the 12-hour period from 6 PM to 6 AM for each week of the 12 weeks of the study.

Due to small numbers, individual activity count time series and collection procedures will be reviewed by the Peace-AD actigraphy team (Drs. [name] and [name], OHSU) for practicability and hypothesis generation. No efficacy analyses will be performed.

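### The model built for the ADCS-CGIC-A is reused for four level scales without their own baseline, and the CMAI wording is unclear; the cost is precision on secondary and exploratory outcomes, not validity

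*SAP*

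**What the plan says.** SAP section 4.1 defines the primary MMRM. The response is "longitudinal ADCS-CGIC-A scores from first post-baseline visit through 12 weeks". The terms are time, intervention, "intervention-by-time interaction plus covariates gender and severity of agitation at baseline defined as CMAI score", and "Time will be treated as categorical". The ADCS-CGIC-A has no baseline score of its own, because it is the clinician's "assessment of change from baseline compared to the ADCS-CGIC-A Baseline Worksheet".

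Section 4.2 carries the model to NPI/NPI-NH total, the key secondary outcome: "An MMRM analysis as described above for the primary outcome measure will compare prazosin vs placebo at 12 weeks". For ADCS-ADL-Severe (Hypothesis 2) and the NPI distress/disruptiveness score (Hypothesis 3) it says: "An MMRM analysis using the model specified for the primary outcome measure above will compare prazosin vs placebo at 12 weeks". Section 4.3 uses the same sentence for the five-domain NPI (Hypothesis 5).

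Two of these hypotheses are worded as change. Hypothesis 3 reads "Participants randomized to prazosin will have a greater reduction in the NPI/NPI-NH" and Hypothesis 5 begins "Improvement in the five domain NPI/NPI-NH subset score". Neither section says whether the modelled response is the score at each visit or its change from baseline.

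For CMAI (Hypothesis 4, section 4.3), the lead-in says the analysis will resemble the primary one, which contains baseline CMAI. The next sentence, which specifies the MMRM, names gender as the only covariate.

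**The concern.** Leaving out an own-baseline term is right for a rating of change. The NPI scores and the ADCS-ADL-Severe are different: they are scored at each visit, and their baseline value is usually among the best predictors of the later value. Because the model takes post-baseline visits only, the baseline does not enter as a response either. Read as written, the plan collects this value and does not use it.

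Section 2 describes a pilot of 25-80 participants, cut from 186 because recruitment was not feasible, and section 1.1 sets 2:1 allocation. Precision cannot be bought back with more patients. The NPI/NPI-NH total is the outcome on which the loss matters most. For CMAI, two analysts following the same text could fit different models.

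**Working it through.** **The plan's own figure.** The point disputes no figure; the pilot size only sets the scale. A two-sample t-test at 2:1, two-sided 5%, 80% power and 0.71 SD needs 72.0 participants. Dividing by 0.90 for 10% dropout gives 80.0, which matches the stated 80 (53 and 27).

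**Inputs.** The SAP gives no correlations, so all three are assumptions, with every variance set to 1:

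- r, own baseline with week 12: 0.3, 0.5, 0.7
- c, baseline CMAI with own baseline: 0.2 to 0.6
- m, baseline CMAI with week 12: either rc (CMAI predicts only through own baseline) or 0.9r (CMAI also predicts independently)

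**Residual variance at week 12.**

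- Raw score, baseline CMAI only: 1 − m²
- Change score, baseline CMAI only: 2 − 2r − (m − c)²
- Own baseline and CMAI, either response: (1 − r² − m² − c² + 2rmc)/(1 − c²)

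| r | c | m | Raw, CMAI only | Change, CMAI only | With own baseline | Cut, raw | Cut, change |
|---|---|---|---|---|---|---|---|
| 0.3 | 0.2 | 0.06 | 0.996 | 1.380 | 0.910 | 9% | 34% |
| 0.3 | 0.6 | 0.18 | 0.968 | 1.224 | 0.910 | 6% | 26% |
| 0.3 | 0.6 | 0.27 | 0.927 | 1.291 | 0.897 | 3% | 30% |
| 0.5 | 0.2 | 0.10 | 0.990 | 0.990 | 0.750 | 24% | 24% |
| 0.5 | 0.6 | 0.30 | 0.910 | 0.910 | 0.750 | 18% | 18% |
| 0.5 | 0.6 | 0.45 | 0.798 | 0.978 | 0.715 | 10% | 27% |
| 0.7 | 0.2 | 0.14 | 0.980 | 0.596 | 0.510 | 48% | 14% |
| 0.7 | 0.6 | 0.42 | 0.824 | 0.568 | 0.510 | 38% | 10% |
| 0.7 | 0.6 | 0.63 | 0.603 | 0.599 | 0.441 | 27% | 26% |

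The third row of each block is most plausible for the five-domain NPI, which measures agitation as the CMAI does.

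**CMAI, if no baseline term is in the model.** With raw scores the cut is r² = 9%, 25%, 49%. With change scores it is 1 − (1 + r)/2 = 35%, 25%, 15%.

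**Net of the extra covariate.** The expected cost of k covariates is a factor 1 + k/(n − k − 3). At n = 80, going from one to two baseline covariates costs (1 + 2/75)/(1 + 1/76) = 1.013. At r = 0.5 with raw scores:

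- High end: 80/(0.758 × 1.013) = 104, so 24 more participants.
- Low end: 80/(0.896 × 1.013) = 88, so 8 more. Charging the full two-covariate factor, 1.027, gives 87, so 7 more.

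At 20:10 the step costs (1 + 2/25)/(1 + 1/26) = 1.04. At r = 0.3 with raw scores the net cut runs from 1 − 0.968 × 1.04 = −1% to 1 − 0.913 × 1.04 = 5%, which is negligible.

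**Single slope or slope by visit.** The figures above need a baseline slope that fits week 12. Suppose instead one common slope per baseline covariate, equally spaced visits, AR(1) decay and m = rc (all assumptions; the SAP states no visit count). The raw-score cut for the reused scales at r = 0.3, 0.5, 0.7 is then 1-3%, 13-19%, 35-45% with three visits. With six visits it is −7%, 7-13%, 33-43%.

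**The case against.** The strongest case against is that nothing here is an error. The stated covariates give a valid comparison, the SAP uses one common severity covariate across outcomes, the primary analysis is untouched, and the trial is now a pilot. This stands, and it limits the point to an improvement in efficiency.

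Second, the text is not equally firm everywhere. NPI total and CMAI carry a lead-in about similar analyses, and the post-baseline wording was written about the ADCS-CGIC-A. A reader could take own baseline as implied. But the specifying sentence for NPI total points back to a model without it, and Hypotheses 2, 3 and 5 adopt that model outright. For CMAI, naming only gender may be a deliberate choice; the two sentences still need reconciling.

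Third, baseline CMAI may recover more than the simplest calculation allows. If it predicts week 12 only through own baseline, the raw-score cut at r = 0.5 is 18-24%. If it also predicts independently, the cut falls to about 10%. This objection is right, and the ranges reported here include it.

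Fourth, in a very small sample a slope per visit costs degrees of freedom for little gain. That is fair at low r with raw scores. With change scores, low r is where the loss is greatest.

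**Conclusion.** The point holds as a free improvement affecting secondary and exploratory outcomes only. Read as written, four models omit own baseline, the response is not stated, and the CMAI covariates are ambiguous.

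With baseline CMAI already in the model, adding own baseline cuts week-12 variance, at assumed r = 0.3, 0.5, 0.7, by about 3-9%, 10-24%, 27-48% for raw scores. For change scores the cut is about 26-34%, 18-27%, 10-26%. Modelling change therefore does not remove the loss. These are illustrations under stated assumptions, not bounds.

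Three stronger readings are not supported:

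- **Bias.** A reader might infer that the comparisons are biased or the primary result weakened. Randomisation keeps them valid, and the ADCS-CGIC-A model is appropriate as it stands.
- **Chance imbalance as a second harm.** A baseline difference of one standard error at 53:27 is √(1/53 + 1/27) = 0.236 SD. Unadjusted, and ignoring CMAI, it shifts a raw-score estimate by r × 0.236 SD. Squared and divided by 0.236², this is r², the same variance loss seen conditionally.
- **A stated loss of power.** The SAP gives no effect size for the NPI or ADL scales, so the variance cut cannot be turned into power for them.

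**What to change.** In sections 4.2 and 4.3, add the outcome's own baseline, alongside gender and baseline CMAI, to the models for NPI/NPI-NH total, distress/disruptiveness, ADCS-ADL-Severe and five-domain NPI. For CMAI, name gender and baseline CMAI as the covariates, so that the two sentences agree.

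Preferably include own baseline by categorical time as well, so that the slope can differ at week 12. If the final sample is very small, this may be reduced to a single baseline slope; the rule for doing so should be written down before unblinding.

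State whether the response is the raw score or change from baseline. Once own baseline is in the model, the treatment estimate is the same either way. Leave the ADCS-CGIC-A model unchanged.

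The cost is one or two sentences and, with the interaction, one slope per visit in each model. No new data are needed: the baseline values are already required for the reductions and improvements that the hypotheses state.

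### Hypothesis 1c compares total rescue lorazepam with no allowance for time on study; if Hypothesis 1d holds, shorter placebo follow-up would shrink a prazosin benefit, modestly near 10% dropout

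*SAP*

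**What the plan says.** Section 4.2 of the SAP sets Hypothesis 1c as "Participants randomized to prazosin will receive a lower cumulative total dose of lorazepam" given as rescue during the trial. On the method it says "Similar analyses to that described for the primary analysis will be performed on the total dose of rescue lorazepam. Multiple linear regression" is then used to compare the arms through 12 weeks, and adds "Gender and severity of agitation at baseline as measured by the CMAI will be included as covariates". No offset, rate outcome, days-on-study term or rule for early leavers is given.

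The next paragraph, Hypothesis 1d, predicts that dropout "due to persistent or worsening intolerable disruptive agitation will occur sooner in the placebo group than in the prazosin group". Participants who leave for drug intolerance are censored there "according to their time from randomization to their last observation on protocol".

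Section 3 makes mITT the primary efficacy set: eligible participants who were "randomized and reached the minimum allowed dose of 1mg BID". Completing 12 weeks is not required. ITT and per-protocol analyses are secondary, and only the per-protocol set requires the 12-week assessments.

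Section 2 assumes 10% dropout overall, without a split by arm, and lists pilot sizes that include 80 (53 and 27) and 40 (27 and 13). Section 4.1 makes no type 1 error adjustment for secondary analyses.

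**The concern.** A cumulative dose grows with time under observation. The plan itself expects that time to be shorter on placebo, yet it compares the totals as if everyone had been followed equally long. The reference to analyses similar to the primary one does not fill the gap: a single total per participant has no repeated visits for an MMRM, and the next words name linear regression.

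What is at stake is interpretation. If prazosin delays agitation dropout, the success of 1d would weaken 1c. A small or null difference in totals could then mean similar rescue use, or only that placebo participants were observed for fewer days. The analysis as written cannot tell these apart.

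**Working it through.** The SAP states no effect size, rate or power for 1c, so there is no figure to reproduce. The size is illustrated under stated assumptions.

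**Step 1: direction.** If dropout is unrelated to rescue use,

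ratio of expected totals = rate ratio × (mean prazosin days ÷ mean placebo days).

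Assume 84 days, dropout of 5% on prazosin and 20% on placebo, and leaving times uniform over the period. Overall dropout at 53/27 is (53 × 0.05 + 27 × 0.20) ÷ 80 = 8.05 ÷ 80 = 10.1%, in line with Section 2.

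- Mean prazosin days: 84 × (1 − 0.05 ÷ 2) = 81.9.
- Mean placebo days: 84 × (1 − 0.20 ÷ 2) = 75.6.
- Ratio shown for a true 0.60: 0.60 × 81.9 ÷ 75.6 = 0.65.

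If nobody in the mITT set leaves before day 14, each leaver loses 35 days on average: 0.60 × (84 − 0.05 × 35) ÷ (84 − 0.20 × 35) = 0.60 × 82.25 ÷ 77 = 0.64.

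**Step 2: dropout that follows rescue need.** This is closer to what 1d describes. Heavy users leave sooner, so more dose is lost than the average days suggest. With 8.3% and 11.3% dropout, the Step 1 formula would turn a true 0.70 into 0.70 × (1 − 0.0415) ÷ (1 − 0.0565) = 0.71. Simulation gives 0.73.

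**Step 3: power by simulation.** All of the following is assumed: personal daily rates gamma-distributed with shape 0.7, times 0.5 mg (placebo mean 0.35 mg/day); a log-linear effect of 0.3 per SD of baseline CMAI; Poisson counts of 0.5 mg units, purely as a simulation device; 84 days; no recording after dropout. In the agitation-driven rows the dropout hazard is proportional to the personal rate. The analysis is least squares on arm, gender and CMAI, two-sided 5%.

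| N | Dropout, prazosin/placebo | True ratio | Ratio on totals | Ratio per day | Power, totals | Power, per day |
|---|---|---|---|---|---|---|
| 80 | none | 0.60 | 0.60 | 0.60 | 42% | 42% |
| 80 | unrelated, 10%/10% | 0.60 | 0.60 | 0.60 | 41% | 42% |
| 80 | unrelated, 5%/20% | 0.60 | 0.65 | 0.60 | 31% | 42% |
| 80 | same, after day 14 only | 0.60 | 0.64 | 0.60 | 33% | 42% |
| 80 | agitation-driven, 8%/11% | 0.70 | 0.73 | 0.70 | 21% | 24% |
| 80 | agitation-driven, 15%/20% | 0.70 | 0.75 | 0.70 | 18% | 24% |
| 80 | agitation-driven, 27%/34% | 0.70 | 0.80 | 0.70 | 14% | 23% |
| 40 | none | 0.60 | 0.60 | 0.60 | 24% | 24% |
| 40 | unrelated, 5%/20% | 0.60 | 0.65 | 0.60 | 18% | 24% |

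Ratios in the no-dropout, equal-dropout and N = 40 rows follow from the Step 1 formula. Runs use 20,000 replicates, or 8,000 for the 15%/20% row. Repeat runs of the 8%/11% row gave 0.73 to 0.74 and 20% to 21% on totals.

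**Step 4: false positives on totals, true ratio 1.0, N = 80.** Rejections favouring prazosin plus rejections favouring placebo:

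- unrelated, 5%/20%: 1.4% + 3.3% = 4.7%;
- agitation-driven, lower dropout: 2.8% + 1.9% = 4.7%;
- agitation-driven, higher dropout: 2.9% + 1.9% = 4.8%.

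**Step 5: does dose per day cure it?** Not fully. Suppose use triples in the last 7 days before dropout. At 5%/20% with equal underlying use, the per-day ratio shows as 0.92, and rejection favouring prazosin is 4.8%, against 2.9% without dropout. If use instead falls steadily over the 12 weeks, the figures are 0.97 and 3.8%. With the pre-dropout rise and agitation-driven dropout near 10%, an underlying 0.70 shows as 0.72 on totals and 0.67 per day, and both have 22% power.

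**The case against.** The strongest reply is that the harm depends on something not shown. If rescue use is recorded to week 12 after discontinuation, the total is a sound outcome, and such recording is commonly a protocol matter. That stands, and it is why the point is conditional.

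Second, the effect is small where it matters most. The fall from 42% to 31% comes from dropout unrelated to rescue use and very unequal between arms. The mechanism that 1d describes costs about three points near 10% dropout, in a test with roughly one chance in four. This also stands.

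Third, the plan already offers context: 1d reports the timing of agitation dropout, and a per-protocol analysis is planned. The first helps a careful reader. The second is not a remedy, because it selects completers: in agitation-driven runs a true 0.70 still showed as about 0.77 there.

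A reader might infer three stronger things that the SAP does not support.

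- *That 1c risks false claims for prazosin.* That would need clearly more intolerance dropout on prazosin. The SAP does not predict it; Hypothesis 1f in Section 5 expects adverse event incidence not to differ.
- *That 1c is badly distorted.* Large distortion needs dropout near one third or a wide gap between arms, and Section 2 plans for 10%.
- *That dose per day should replace the total.* Step 5 shows that it can err towards prazosin, and it would change the stated hypothesis.

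**Conclusion.** The point holds as a modest, optional improvement. As written, 1c has no allowance for time on study, in an analysis set that keeps early leavers, while 1d predicts shorter placebo follow-up. If 1d is right and rescue use is not recorded after discontinuation, a prazosin benefit on totals is attenuated: slightly when agitation-driven dropout is near 10%, and materially when dropout approaches one third or is much more unequal. Equal dropout does no material harm. The expected error is conservative for prazosin, and the primary analysis is not touched.

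The direction follows from the SAP's own hypotheses. The sizes rest entirely on assumed rescue rates, dropout by arm and dropout mechanism. Confidence in the size is therefore moderate at best.

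**What to change.** In the 1c paragraph of Section 4.2:

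- Keep the cumulative total as the stated outcome.
- Prespecify beside it the same regression, with gender and baseline CMAI, on rescue dose per day on study. Count days from randomization to the last on-protocol observation, the time that 1d already uses for censoring.
- Report mean days on study by arm.
- State that a null or small difference in totals is not read as similar rescue use when the per-day result or days on study differ by arm, and that neither result is read alone.
- State whether rescue use is recorded to week 12 regardless of discontinuation. If it is, the total stands alone and the per-day analysis is unnecessary.

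The cost is a few sentences and no new data, since dose is needed for 1c and time on study for 1d. The downsides are one more unadjusted secondary analysis, noisier daily rates for those followed briefly, and a per-day result that can overstate a prazosin benefit if use rises just before dropout.
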